### **1.5. Compliance**

This study will be conducted in compliance with this protocol, Good Clinical Practice (GCP), and all applicable regulatory requirements.

## **2. OBJECTIVES**

The primary objective of this study is:

- To observe the long-term safety of filgotinib in subjects who have completed or met protocol specified efficacy discontinuation criteria in a prior filgotinib treatment study for CD

The secondary objective of this study is:

- To evaluate the effect of filgotinib on PRO2 and CDAI scores

[REDACTED]

[REDACTED]

[REDACTED]

[REDACTED]

[REDACTED])

## **3. STUDY DESIGN**

### **3.1. Endpoints**

The primary end point is:

- Safety, evaluated through AEs, clinical laboratory tests, and vital signs

The secondary end points are:

- Change from baseline in PRO2 and CDAI scores

[REDACTED]

[REDACTED]

[REDACTED]

[REDACTED]

[REDACTED]

### 3.2. Study Design

This is a long-term extension study to evaluate the safety of filgotinib administered to subjects with CD.

This study includes:

- Day 1
- Treatment Visits: Week 2, Week 4, Week 12, and then every 12 weeks thereafter until filgotinib becomes commercially available in the country or until the end of study (31 January 2025), whichever comes first..
- PTx safety assessments (30 days after the last dose of study drug) for subjects who complete all study treatment visits or discontinue early. All subject visits, including the PTx visit, must be completed by 31 January 2025 at the latest.

### 3.3. Study Treatments

This is a long-term extension study. Some subjects will receive open-label drug and some will receive blinded dosing until subject's treatment in the corresponding parent study is unblinded. In general, subjects who fully complete a parent study blinded will continue blinded dosing at the same regimen in the present study on 200 mg filgotinib, 100 mg filgotinib, or placebo. After the corresponding parent study (GS-US-419-4015, GS-US-419-4016, or GS-US-419-3895, or other Gilead/ Galapagos-sponsored filgotinib treatment study) is unblinded, subjects enrolled in the present study may be unblinded. Subjects who enroll from a parent study and receive blinded treatment in the DIVERSITY LTE study will have their DIVERSITY LTE treatment assignment unblinded when the parent study is unblinded. Subjects will continue on the same dose of open-label filgotinib as they had been receiving in blinded treatment. Subjects on placebo treatment will discontinue study drug and study participation. Subjects who exit a parent study due to disease worsening or failure to meet response or remission criteria will receive open-label 200 mg filgotinib, with the exception of US and Korea males in this category who were not considered biologic refractory who will receive open-label 100 mg filgotinib. Subjects enrolled from other filgotinib treatment studies for CD will receive open-label 200 mg filgotinib daily.

For the purposes of this study, the definition of dual (or biologic) refractory includes subjects who:

- 1) Failed any TNF $\alpha$  antagonist and vedolizumab at the time of randomization in studies GS-US-419-3895, GS-US-419-4015, and GS-US-419-4016, or
- 2) Failed any TNF $\alpha$  antagonist and are taking vedolizumab at the time of randomization into the GS-US-419-4016 study.

Details on dosing regimen for LTE are noted below in [Table 3-1](#).

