### **1.3. Rationale for This Study**

A need for safer, better tolerated, durable efficacious therapies for patients with CD exists. Despite significant uptake in the use of anti-TNF agents, tolerability of anti-TNFs due to allergic and autoimmune reactions, lack of durable response, and significant increased risk of infection remain problematic. Filgotinib is a once daily, oral therapy that may prove efficacious without the risk of allergic and autoimmune phenomena observed with anti-TNF agents.

This is a long-term extension study (GS-US-419-3896; Galapagos Study ID GLPG0634-CL-310 [DIVERSITY LTE]) to provide treatment with filgotinib for subjects with moderately to severely active CD (who have completed or met protocol specified efficacy discontinuation criteria in a prior filgotinib treatment study for CD) until filgotinib becomes commercially available in the country or until the end of study (31 January 2025), whichever comes first..

The purpose of this study is to observe the safety of long-term therapy and to ensure continued access to study drug for subjects who responded in the parent protocol of filgotinib. In addition, the study provides an open-label alternative at the highest possible dose (excluding males who are not dual-biologic refractory in the US and Korea, refer to Section 3.3 for further information) for subjects who had disease worsening or lack of response in the parent study.

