### 1.3.1. Rationale for Dose

In Phase 2 trials in RA, pooled data with an exposure – response analysis demonstrated a dose-dependent increase in efficacy up to 200 mg total daily dose. In the Phase 2 study of CD, subjects treated in the 200 mg arm showed favorable response and remission rates (47% remission over 23% placebo and 59% response over 41% placebo). Remission rates at Week 20 for subjects who failed placebo for the first 10 weeks and commenced 100 mg from Weeks 10 to 20 was slightly lower (32%) though response rate was comparable (59%), indicating some level of efficacy at the 100 mg dose. These results are consistent with the relationship observed between filgotinib exposures and inhibition of pSTAT1 activation (ex-vivo) following single and multiple filgotinib doses, where maximal inhibition of pSTAT1 activation (~78%) was achieved at or above 200 mg total daily dose and intermediate inhibition (~47%) at 100 mg {[Namour 2015](#)}. pSTAT1 data, in conjunction with considerations around the margin for nonclinical testicular findings, suggests assessing doses above 200 mg is not indicated. The presence of response in CD subjects in the exploratory 10 to 20 week arm of Study GLPG0634-CL-211, and study of multiple doses (ie, 100 mg and 200 mg once daily) in the present study will enable establishment of an appropriate nominal dose and determine the dose with the most favorable risk/benefit profile for CD subjects. The present study will ensure continued access to blinded dosing for specific subjects (those who complete a respective parent protocol through the end of that study). After the corresponding parent study (GS-US-419-4015, GS-US-419-4016, or GS-US-419-3895 [Galapagos Study ID: GLPG0634-CL-309]) is unblinded, subjects enrolled in the present study may be unblinded. Subjects who enroll from a parent study and receive blinded treatment in the DIVERSITY LTE study will have their DIVERSITY LTE treatment assignment unblinded when the parent study is unblinded. Subjects will continue on the same dose of open-label filgotinib as they had been receiving in blinded treatment. Subjects on placebo treatment will discontinue study drug and study participation. In addition, the present study allows open-label access at the highest possible dose for subjects who were non-responders or experienced disease worsening on blinded dosing in a parent study. At no time will males in the US and Korea who are not dual biologic refractory receive 200 mg.

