#### 1.4. Risk/Benefit Assessment for the Study

Crohn's disease is a progressive and potentially life-threatening disease with few treatment options, many of which result in primary or secondary nonresponse. Inflammatory bowel disease may lead to increased risk of gastrointestinal malignancies, impairment in quality of life, and ultimate need for life-altering surgery. Current treatment options are limited in ability to establish mucosal healing and clinical remission and have significant safety and efficacy limitations; for example, biologics have significant immunogenic risks and steroids are associated with increased morbidity and mortality. Remission rates are generally low when compared to placebo rates across most therapies for IBD. There remains substantial unmet need in IBD, particularly in moderate to severe disease. The lifelong nature of IBD increases the probability that subjects have cycled through various therapies, leaving few approved options.

Nonclinical studies in rats and dogs identified lymphoid tissues and testes as target organs for filgotinib in long-term repeat-dose toxicity studies. Although decreased lymphocyte numbers observed in nonclinical studies have not been seen in clinical studies, hematological assessment will be performed throughout the present study to ensure this potential risk is appropriately monitored. In both rats and dogs, microscopic findings in the testes included germ cell depletion and degeneration, with reduced sperm content and increased cell debris in the epididymis and reduction in fertility in male rats. The dog was determined to be the most sensitive species. When using the (AUC at the NOAELs for dogs in the 26-week and 39-week chronic toxicity studies, and the 39 week targeted exposure toxicity study, the exposure margins compared with the highest proposed clinical dose of 200 mg once daily are 2.5, 1.9 and 3.6-fold respectively, in subjects with CD. A male safety study is planned to examine the potential effect of filgotinib on sperm/ejaculate parameters. Pending those results, the use of 200 mg in males in the US and Korea with CD or UC will be limited to subjects who have failed at least two biologic therapies (any TNF $\alpha$  antagonist and vedolizumab). Refer to the IB for further information about nonclinical and clinical testicular findings.

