**Table 3-1. Dosing Regimens in LTE**

Dose in parent study	Reason for exiting parent study	Dose in LTE	Dose in LTE after LTE Unblinding
All Females, Non-US males and US & Korea dual refractory males			
200 mg filgotinib, blinded	Study completed to end	200 mg filgotinib + PTM 100 mg (blinded dosing)	200 mg filgotinib, open-label
100 mg filgotinib, blinded	Study completed to end	100 mg filgotinib + PTM 200 mg (blinded dosing)	100 mg filgotinib, open-label
Placebo, blinded	Study completed to end	PTM 100 mg + PTM 200 mg (blinded dosing)	Discontinue study drug
200 mg filgotinib, open-label/ blinded	Completed treatment up to primary endpoint	200 mg filgotinib, open-label	200 mg filgotinib, open-label
Placebo, open-label/ blinded	Completed treatment up to primary endpoint	200 mg filgotinib, open-label	200 mg filgotinib, open-label
200 mg filgotinib, blinded	Disease worsening and/or failure to meet response/remission criteria	200 mg filgotinib, open-label	200 mg filgotinib, open-label
100 mg filgotinib, blinded	Disease worsening and/or failure to meet response/remission criteria	200 mg filgotinib, open-label	200 mg filgotinib, open-label
Placebo, blinded	Disease worsening and/or failure to meet response/remission criteria	200 mg filgotinib, open-label	200 mg filgotinib, open-label
200 mg filgotinib, open-label	Study completed to end	200 mg filgotinib, open-label	200 mg filgotinib, open-label
100 mg filgotinib, open-label	Study completed to end	100 mg filgotinib, open-label	100 mg filgotinib, open-label
200 mg filgotinib, open-label	Disease worsening and/or failure to meet response/remission criteria	200 mg filgotinib, open-label	200 mg filgotinib, open-label
100 mg filgotinib, open-label	Disease worsening and/or failure to meet response/remission criteria	200 mg filgotinib, open-label	200 mg filgotinib, open-label

Dose in parent study	Reason for exiting parent study	Dose in LTE	Dose in LTE after LTE Unblinding
US & Korea Males who have not failed at least two biologic therapies (any TNF<math>\alpha</math> and vedolizumab)			
100 mg filgotinib, blinded	Study completed to end	100 mg filgotinib (blinded dosing)	100 mg filgotinib, open-label
Placebo, blinded	Study completed to end	PTM 100 mg (blinded dosing)	Discontinue study drug
100 mg filgotinib, blinded	Disease worsening and/or failure to meet response/remission criteria	100 mg filgotinib, open-label	100 mg filgotinib, open-label

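### The dose rule for subjects from other filgotinib Crohn's studies gives 200 mg without the US/Korea male exception, contradicting the protocol's own ban

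*Protocol*

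**What the plan says.** Below, a restricted male means a US or Korean male who is not dual biologic refractory.

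- **The ban.** Section 1.3.1 states it absolutely: "At no time will males in the US and Korea who are not dual biologic refractory receive 200 mg". Section 1.4 states it generally, requiring failure of two or more biologics: "the use of 200 mg in males in the US and Korea with CD or UC will be limited to subjects who have failed". Section 1.3 repeats it for the open-label option after worsening or non-response: "excluding males who are not dual-biologic refractory in the US and Korea".
- **The dose rule.** Sections 1.3.1 and 3.3 carry the same sentence: "Subjects enrolled from other filgotinib treatment studies for CD will receive open-label 200 mg filgotinib daily". Neither copy has a qualifier for sex, country or refractory status.
- **The exception.** In Section 3.3, the sentence on exits for worsening or non-response gives 200 mg "with the exception of US and Korea males in this category who were not considered biologic refractory who will receive open-label 100 mg filgotinib". The words tying it to that category confine it to those exits.
- **The table.** Table 3-1 has two blocks. The exit "Completed treatment up to primary endpoint" appears only in the first block. The second block, for restricted males, has no such row.
- **Where the dose comes from.** Section 6.1 refers to Section 3.3 for the dosing regimen.

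**The concern.** The limit is a safety measure. Section 1.4 bases it on testicular findings in rats and dogs, with exposure margins in dogs of 1.9- to 3.6-fold at 200 mg, and applies it pending a male safety study. The protocol history records that the Korean limit followed a request from the Korean regulator. A site that turns to the section named as the source of the dose would find 200 mg for a restricted male coming from another study, and would not find the absolute ban there.

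Eligibility does not close the gap. Section 4.2 admits subjects from any other sponsored filgotinib Crohn's study without a sex or country limit. The clause in Section 7.6 preferring the more conservative criterion concerns toxicity management and does not govern dose assignment.

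**Working it through.** No calculation applies, so the check sets the texts side by side.

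**Step 1: count the rows of Table 3-1.**

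| Block | Rows | LTE dose 200 mg | 100 mg | Placebo | Primary-endpoint rows |
|---|---|---|---|---|---|
| First (females, unrestricted males) | 12 | 9 | 2 | 1 | 2, both 200 mg |
| Second (restricted males) | 6 | 0 | 5 | 1 | 0 |

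Check: 9 + 2 + 1 = 12 and 0 + 5 + 1 = 6.

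**Step 2: trace a restricted male by route out of another Crohn's study.** Section 6.2.1 counts a subject from such a study as completed in either of two ways: all visits and procedures done, or treatment up to the primary endpoint.

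| Route | Section 3.3 text | Table 3-1 | Sections 1.3.1 and 1.4 |
|---|---|---|---|
| Treated to primary endpoint, US | 200 mg; exception does not apply | No row | Not 200 mg |
| Treated to primary endpoint, Korea | 200 mg; exception does not apply | No row in second block; 200 mg if the first-block heading is read literally | Not 200 mg |
| All visits done | 200 mg; exception does not apply | Second block: 100 mg or placebo | Not 200 mg |
| Worsening or non-response | 100 mg by the exception | Second block: 100 mg | Not 200 mg |

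**Step 3: read the result.** The last route is consistent. On the primary-endpoint route, the 200 mg sentence is the only text that assigns the US male a dose, and it assigns the one the ban forbids. The all-visits route also meets the unqualified sentence. However, its clash with the completed-to-end rows is not peculiar to restricted males: the first block has completed-to-end rows giving 100 mg or placebo too. That clash raises the general question of whether those rows apply to other studies at all.

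**Step 4: the first-block heading.** It begins "All Females, Non-US males and US" and goes on to add Korean dual-refractory males. Read literally, its non-US males include restricted Korean males. This matters mainly for the two primary-endpoint rows, because the second block offers no competing row there.

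**Step 5: a likely origin.** The summary of changes for Amendment 9 lists Sections 1.3.1 and 3.3 among those altered to admit subjects from other studies. SAP Section 1.2, based on Amendment 8, describes the dosing without the 200 mg sentence. This fits a new entry route written without carrying the older limit across, though that is inference.

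**The case against.** The strongest reply is that the ban is already there and absolute. In Section 1.3.1 the 200 mg sentence comes directly after it, and the next sentence sends the reader to Section 3.3 for the meaning of dual refractory. A general dose rule under an absolute limit is a natural reading, and it settles what the sponsor intended. It does not cure Section 3.3, which repeats the dose rule without the ban and attaches its only exception to a different group.

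A second reply is that the missing rows may be correct. The two primary-endpoint rows list only 200 mg and placebo as parent dose, and Section 1.4 words the limit more widely than this study. A 200 mg versus placebo study observing that limit may have enrolled no restricted males. This is plausible and is why the number affected may be zero, but the documents do not confirm it.

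On Table 3-1, a reader might infer that the heading puts restricted Korean males on 200 mg more widely, since three of the six second-block rows (100 mg blinded, placebo blinded and 100 mg open-label) have first-block counterparts at 200 mg. The documents do not support that. All three are exits for worsening or non-response, for which Section 3.3 expressly gives restricted males 100 mg. The second-block heading also names Korean males, and adding Korea to the first heading would be redundant if every Korean male already belonged there.

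The dual-refractory definition gives a time point only "at the time of randomization in studies GS-US-419-3895, GS-US-419-4015, and GS-US-419-4016", with a further limb for vedolizumab users in the last of these. Other studies have none. This is minor, because Section 1.4 and the second-block heading describe failure without reference to a particular study.

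**Conclusion.** The point holds as an internal contradiction in the operative dosing text. It concerns restricted males who completed another filgotinib Crohn's study, and it is clearest for those treated to the primary endpoint. It is worth correcting because the rule it breaks is a safety-based dose cap.

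A reader might infer that the protocol now permits 200 mg in these men, or that some have received it. Neither follows. The wording of the ban shows that it was meant to govern. Actual assignment runs through the IWRS and the rollover manual, whose rules are not in the documents. The number affected is not stated and may be zero. The planned analysis is unaffected, because SAP Section 3.2 groups subjects by actual treatment received.

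The conclusion assumes that the ban still stands for this entry route; nothing in the protocol says it was lifted.

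**What to change.** 1. In Sections 1.3.1 and 3.3, add to the 200 mg sentence an exception for US and Korea males who are not dual biologic refractory, giving them open-label 100 mg. If the sponsor has in fact lifted the limit for this route, amend Sections 1.3, 1.3.1 and 1.4 instead.
2. Add the matching primary-endpoint rows, at open-label 100 mg, to the restricted-male block of Table 3-1.
3. Confirm that the IWRS assignment agrees.
4. As a tidy-up, reword the first-block heading to non-US/non-Korea males.
5. The sponsor should choose and state when dual-refractory status is judged for other studies. Entry to the parent study and entry to the extension are both possible.

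The cost is one clause used twice, a few table rows, a heading, a definition line and a system check, with no added visits or procedures. It needs ethics approval under Section 9.2.1 and can go into the next amendment.

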**Table 3-1. Dosing Regimens in LTE**

Dose in parent study	Reason for exiting parent study	Dose in LTE	Dose in LTE after LTE Unblinding
All Females, Non-US males and US & Korea dual refractory males			
200 mg filgotinib, blinded	Study completed to end	200 mg filgotinib + PTM 100 mg (blinded dosing)	200 mg filgotinib, open-label
100 mg filgotinib, blinded	Study completed to end	100 mg filgotinib + PTM 200 mg (blinded dosing)	100 mg filgotinib, open-label
Placebo, blinded	Study completed to end	PTM 100 mg + PTM 200 mg (blinded dosing)	Discontinue study drug
200 mg filgotinib, open-label/ blinded	Completed treatment up to primary endpoint	200 mg filgotinib, open-label	200 mg filgotinib, open-label
Placebo, open-label/ blinded	Completed treatment up to primary endpoint	200 mg filgotinib, open-label	200 mg filgotinib, open-label
200 mg filgotinib, blinded	Disease worsening and/or failure to meet response/remission criteria	200 mg filgotinib, open-label	200 mg filgotinib, open-label
100 mg filgotinib, blinded	Disease worsening and/or failure to meet response/remission criteria	200 mg filgotinib, open-label	200 mg filgotinib, open-label
Placebo, blinded	Disease worsening and/or failure to meet response/remission criteria	200 mg filgotinib, open-label	200 mg filgotinib, open-label
200 mg filgotinib, open-label	Study completed to end	200 mg filgotinib, open-label	200 mg filgotinib, open-label
100 mg filgotinib, open-label	Study completed to end	100 mg filgotinib, open-label	100 mg filgotinib, open-label
200 mg filgotinib, open-label	Disease worsening and/or failure to meet response/remission criteria	200 mg filgotinib, open-label	200 mg filgotinib, open-label
100 mg filgotinib, open-label	Disease worsening and/or failure to meet response/remission criteria	200 mg filgotinib, open-label	200 mg filgotinib, open-label

Dose in parent study	Reason for exiting parent study	Dose in LTE	Dose in LTE after LTE Unblinding
US & Korea Males who have not failed at least two biologic therapies (any TNF<math>\alpha</math> and vedolizumab)			
100 mg filgotinib, blinded	Study completed to end	100 mg filgotinib (blinded dosing)	100 mg filgotinib, open-label
Placebo, blinded	Study completed to end	PTM 100 mg (blinded dosing)	Discontinue study drug
100 mg filgotinib, blinded	Disease worsening and/or failure to meet response/remission criteria	100 mg filgotinib, open-label	100 mg filgotinib, open-label
Placebo, blinded	Disease worsening and/or failure to meet response/remission criteria	100 mg filgotinib, open-label	100 mg filgotinib, open-label
100 mg filgotinib, open-label	Study completed to end	100 mg filgotinib, open-label	100 mg filgotinib, open-label
100 mg filgotinib, open-label	Disease worsening and/or failure to meet response/remission criteria	100 mg filgotinib, open-label	100 mg filgotinib, open-label

Abbreviations: LTE=long-term extension; PTM=placebo-to-match

### 3.4. Duration of Treatment

Subjects will receive filgotinib or placebo until filgotinib becomes commercially available in the country or until the end of study (31 January 2025), whichever comes first. All subject visits, including the PTx visit, must be completed by 31 January 2025 at the latest. The maximum treatment duration will be approximately 7.5 years.

### 3.5. Criteria for Study Drug Interruption or Discontinuation

#### 3.5.1. Study Drug Interruption Considerations

The medical monitor should be consulted prior to study drug interruption when medically feasible.

Study drug interruption should be considered in the following circumstances; prior to resumption of study drug, the investigator should discuss the case with the medical monitor:

- Intercurrent illness that would, in the judgment of the investigator, affect assessments of clinical status to a significant degree.
- Subject is scheduled for elective or emergency surgery (excluding minor skin procedures under local or no anesthesia); timing of study drug pausing should be determined in consultation with the medical monitor.
- Any subject who develops a new infection during the study should undergo prompt and complete diagnostic testing appropriate for an immunocompromised individual, and the subject should be closely monitored.

- Subjects with newly positive (converted) or 2 indeterminate QuantiFERON® TB test (or centrally reported equivalent assay) result(s) should interrupt study drug dosing and be evaluated for active TB and latent TB by the investigator per local standard of care. An indeterminate result should be repeated once and the second result (if positive or negative) will be accepted. Positive or negative results must not be repeated.
- Subjects diagnosed with latent TB (ie, a subject who has newly identified positive diagnostic TB test result, in which active TB has been ruled out) may initiate an adequate course of prophylaxis as per local standard of care; appropriate, ongoing, prophylactic treatment for latent TB must be initiated for a minimum of 4 weeks prior to the continuation of study medication. Subjects may resume study drug after investigator's consultation with medical monitor.
- Subjects with positive or 2 indeterminate QuantiFERON® test result(s) who are determined as having neither latent nor active TB infection may continue participation in the study after consultation and approval from medical monitor. Any subject with active TB must be discontinued from the study. Subjects who were previously treated for TB with a complete and adequate course of therapy as per local standard of care and as verified by the investigator do not need to have yearly QuantiFERON® tests. Subjects previously treated for TB should be screened at least yearly for signs and symptoms consistent with reactivation of TB. Any subject with active TB should be discontinued from the study.
- After a confirmed laboratory change representing moderate renal impairment (estimated creatinine clearance [CrCl]  $\geq 35$  mL/min and  $< 60$  mL/min per Cockcroft-Gault [CC&G] formula) at any time during the study, the following actions should be taken by the investigator and documented:
  - Establish possible underlying condition and initiate appropriate action to resolve.
  - Retest CrCl within 8 weeks.
  - Carefully consider individual benefit/risk of continuation of filgotinib 200 mg once daily in relation to the observation.
  - If continuation of filgotinib 200 mg once daily is not considered appropriate, interrupt treatment until retest confirms CrCl  $\geq 60$  mL/min.
  - The investigator/designee should assess individual subject benefit/risk with regards to re-initiation of treatment after repeat or prolonged interruptions, or if re-initiation is not considered appropriate.
- For subjects with confirmed absolute lymphocyte count (ALC) less than 500 cells/mm^3, retest within 3 to 7 days, filgotinib should be interrupted until grade returns to  $\leq$  Grade 2 (more than 500 cells/mm^3). If ALC does not return to  $\leq$  Grade 2 within 4 weeks or returns to less than 500 cells/mm^3 following re-challenge with filgotinib, then filgotinib should be permanently discontinued and the subject managed according to local practice.

*NOTE: During the time of study drug interruption for any of the above, the subject may continue to have study visits and to take part in procedures and assessments, if deemed medically appropriate by the investigator.*

The medical monitor should consult the medical leader as needed.

